Study objectives:	
 1. Comparative assessment of efficacy of Primapur[®] (follitropin alfa), a solution for subcutaneous administration, and GONAL-F[®] (follitropin alfa). 2. Comparative assessment of safety of Primapur[®] (follitropin alfa), a solution for subcutaneous administration, and GONAL-F[®] (follitropin alfa).
Study design:	
multicenter randomized embryologically blinded parallel group comparative therapeutic equivalence study of Primapur[®], a solution for subcutaneous administration, and GONAL-f[®], a solution for subcutaneous administration.

Planned number of patients	
110 female patients randomized into two equal groups of 55 subjects receiving study referenced drugs.

Study centers	
3 specialized medical centers in the Russian Federation

Study population:	
Women aged 20-35 with established causes of infertility (tubal factor, male factor (oligoasthenoteratozoospermia) and indications for the use of assist reproductive technologies (ART).

Inclusion criteria:	
 1. Women with established causes of infertility and indications for the use of ART methods, according to the Order of the Ministry of Health of the Russian Federation "On the use of assisted reproductive technologies, contraindications and limitations to their use" No. 107 n dated August 30, 2012. 2. Causes of infertility: Tubal factor and/or male factor (oligoasthenoteratozoospermia). 3. Female patients aged 20 to ≤35 with an independent regular menstrual cycle (duration: 21 to 35 days); 4. First or second attempt of IVF/ICSI.

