
Period of PI/PR therapy. Up to 15 days (2 weeks and 1 day).
	
Visit 2. Randomization. Day 1. Beginning of the stimulation protocol (2-3 day of the menstrual cycle)
 
 1. Selection criteria check. Decision of randomization into a clinical study or registration of a screening failure. 2. Carrying out randomization, using IWRS, distribution into groups: group FSG031 of Primap[®], a study drug, or group FSG032 of GONAL-f[®], a reference drug. 3. Inspection: 
 ✓ Registration of patient complaints. ✓ Registration of changes in concurrent conditions and concomitant therapy. ✓ Physical examination ✓ Measurement of vital parameters, particularly HR, BP, RR, body temperature. ✓ Prescription of the stimulation protocol. 4. Introduction of the 1st dose of PI/PR. 5. Registration of adverse events/reactions after the first dose of PI/PR. 
Visit 3. Day 5-8 of stimulation.
 
The 3rd visit procedures are aimed at a primary evaluation of the therapy efficacy. The patient may be invited to conduct the procedure once (on the 5th day) or several times (additionally on the 6th, 7th, 8th days of the therapy) at the investigator's discretion, depending on the results of the required diagnostic procedures. 3 visit procedures:
 
 1. Instrumental examinations: 
 ✓ Transvaginal ultrasound of ovaries. Follicle count and determination of follicle diameter in both ovaries. 2. Inspection: 
 ✓ PI/PR dose adjustment (in the absence of follicles more than 10 mm on 5-8 days of stimulation).

- ✓ Registration of patient complaints, concurrent conditions and concomitant therapy.
 - ✓ Physical examination
 - ✓ Measurement of vital parameters, particularly HR, BP, RR, body temperature.
3. *Exclusion of the patient from the study in case of failed stimulation (with no response to FSH administration on day 5-8 of stimulation).*
 4. Initiation of GnRH antagonist administration (when the lead follicle is about 14 mm);
 5. Registration of adverse events/reactions.

Additional visit for GnRH antagonist administration (if required).

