
Follow-up period. 10 weeks.
	
Visit 5. Puncture of follicles. IVF/ICSI. No more than 37 hours from the introduction of the ovulation inducer (Visit 4).
 
 1. Examination before follicle puncture: 
 ✓ Registration of patient complaints. ✓ Registration of changes in concurrent conditions and concomitant therapy. ✓ Physical examination ✓ Measurement of vital parameters. 2. Blinding of the studied therapy at the stage of oocyte counting performed by the embryologist (by coding the data on the study drugs in the patient's electronic medical record viewed by the embryologist). 3. Puncture of follicles: 
 ✓ Ultrasound. Follicle count before anesthesia and follicle puncture. ✓ USG-guided puncture of follicles under general anesthesia. ✓ Obtained oocyte counting performed by the embryologist. 4. Carryinh out of IVF/ICSI. 
 ✓ Determination of the number of mature/immature oocytes. 5. Registration of adverse events/reactions. 6. Exclusion of the patient from the study if cryopreservation of embryos is required according to the indications. 
Visits 6 and 7: Transfer of the embryo(s)/blastocyst(s) into the uterine cavity. Up to 5 days after Visit 5.
 
 1. Inspection: 
 ✓ Registration of patient complaints. ✓ Registration of changes in concurrent conditions and concomitant therapy. ✓ Physical examination ✓ Measurement of vital parameters, particularly HR, BP, RR, body temperature. 2. USG-guided transfer of embryos/blastocysts (1 or 2, but not more than 2). 3. Registration of adverse events. 4. Exclusion of the patient from the study if cryopreservation of embryos is required according to the indications.

Telephone contact. Day 7 from embryo/blastocyst transfer.

1. Registration of patient complaints, changes in concurrent conditions and concomitant therapy. State assessment.
2. Registration of adverse events.

Visit 8: Confirmation of biochemical pregnancy/early study termination. Day 12-17 from embryo/blastocyst transfer.

1. Laboratory testing:
 - ✓ hCG blood test.
2. Inspection:
 - ✓ Registration of patient complaints.
 - ✓ Registration of changes in concurrent conditions and concomitant therapy.
 - ✓ Physical examination
 - ✓ Measurement of vital parameters.
3. Registration of adverse events.

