Unscheduled visit.	
At any stage of the study, an additional visit to the center can be made at the investigator's discretion if a patient has a complaint requiring a reproductologist's intervention for the purpose of individually monitoring the superovulation induction course and monitoring the pregnancy course in order to reduce the risk of developing any adverse reaction and to monitor the therapy efficacy.
 
Additional visits may include, but not be limited to, the following procedures (depending on the indications):
 
 1. Instrumental examinations: 
 ✓ Transvaginal ultrasound of ovaries. 2. FSH dose adjustment. 3. Physical examination. 4. Measurement of vital parameters. 5. Registration of patient complaints. 6. Complete blood count. 7. Biochemical blood test. 8. Coagulogram. 9. General urine analysis.

	10. Blood test for hormones and other clinically relevant markers.

*The presence of anti-FSH antibodies will be determined centrally at the laboratory of Exacte Labs LLC and/or an additional research laboratory on a contractual basis (if required). The study results will be attached to the initial documentation of the investigation site. Immunogenicity will be evaluated using the following methods: enzyme immunoassay and surface plasmon resonance for positive samples.
	

Efficacy evaluation criteria:
	
Study endpoints per patient:
 
Primary point:
 
 • Total number of aspirated oocytes. 
Secondary points:
 
 • Number of follicles \geq 16 mm on the day of administration of hCG. • Number of mature oocytes (MII stage). • Number of fertilized oocytes. • Number of patients with embryo transfer (days 2-3). • Number of patients with blastocyst transfer (days 4-5). • Total dose of a human rFSH product injected (IU). • Number of days of stimulation. • Percentage of patients who needed a FSH dose adjustment on the 5th-8th day of stimulation. • Number of patients who abandoned the IVF/ICSI program in the process of stimulation. • Number of non-responders to stimulation. • Incidence of biochemical pregnancies. • Incidence of clinical pregnancies (up to 10 weeks after the embryo(s) transfer).

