
Statistical processing of data:
	
Description of methods of statistical data processing
 
The quantitative data obtained during the study will be tested for normal distribution, using the Shapiro-Wilk test and, if necessary, the F-test of equality of variances. For variables corresponding to the normal distribution, mean values and standard deviation of the mean will be calculated; Quantitative data not corresponding to the normal distribution will be described using the median and interquartile interval. Qualitative variables will be described using absolute and relative frequencies (percentages).
 
In order to compare two groups of normally distributed quantitative data, the Student's t-test will be used; if quantitative data distribution differs from normal values, the Mann-Whitney U test will be used. For intergroup comparisons by qualitative characteristics, the Fisher's exact test will be used; correction of p-value in the case of multiple hypotheses will be realized through the Bonferroni adjustment.
 
Applicable significance level
 
In this study, the indicators are considered statistically significant at the bilateral p-value level <0.05.
 
Therapeutic equivalence criteria.
 
The conclusion about the therapeutic equivalence of the two drugs will be made if the difference between the mean values of the total number of oocytes obtained when applying both drugs lies within the limits of the equivalence threshold (± 3.4 oocytes).
 
Procedures for accounting of missing, not-analyzable and uncertain data.
 
CRF information will be entered into the computer database, and data will be electronically and visually verified for completeness, and allowable ranges will be checked. All errors detected during the quality control process will be corrected. In the presence of deviating data ("outliers"), the correctness of their measurement and introduction into the database will be rechecked. Data will be analyzed twice: with and without "outliers". If the results are stable to the "outliers", a calculation that includes all available values of the variable will be used. If there is the influence of "outliers" on the initial result, the results obtained both taking into account the deviating data and without deviating data will be presented and commented on.

Calculation of sample size

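### The primary comparison has no center term and the documents do not say whether randomization is stratified by center; the cost is precision, not bias

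*Combined protocol and SAP*

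**What the plan says.** All references are to the combined protocol and SAP.

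- **Size and sites.** Planned number of patients: "110 female patients randomized into two equal groups of 55 subjects". Study centers: "3 specialized medical centers in the Russian Federation".
- **Allocation.** Visit 2, item 2: "Carrying out randomization, using IWRS, distribution into groups". No stratification factor, block size or per-center list is named here or elsewhere. Nothing says that stratification is not used.
- **Endpoint.** Efficacy evaluation criteria: "Total number of aspirated oocytes", per patient. Visit 5 describes how it arises: "USG-guided puncture of follicles under general anesthesia", then "Obtained oocyte counting performed by the embryologist". The embryologist is blinded to product.
- **Central work.** Central testing is stated for antibodies only: "The presence of anti-FSH antibodies will be determined centrally at the laboratory of" a named laboratory. No central oocyte count is described.
- **Analysis.** Statistical processing of data: "In order to compare two groups of normally distributed quantitative data, the Student's t-test will be used", with Mann-Whitney as the alternative for non-normal data. The therapeutic equivalence criterion compares the difference between the two means with ±3.4. It names no confidence interval and no center adjustment.

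**The concern.** The number of oocytes retrieved depends on who aspirates and who counts. Some steps before retrieval are also left to the investigator, namely the extra Visit 3 assessments and the timing of the additional antagonist visit. With three centers, mean yield may well differ between them.

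If so, two things follow from leaving center out. Without stratification, the arms can differ by chance in their mix of centers, and that difference becomes part of the noise in the treatment comparison. With stratification, the arms are balanced on center, but an unadjusted test still counts center variance in its standard error and so overstates the uncertainty. In both cases the interval to be compared with ±3.4 is wider than the data require. The design has little precision to spare, since its 80% power assumes a true difference of exactly zero.

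**Working it through.** **Inputs from the documents:** 3 centers; 55 per group; SD 6; margin d = 3.4; α = 0.05, applied to each one-sided test as in the sample size formula; power at least 80%.

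**Assumptions, because the documents give no center effect:** three roughly equal centers with means −R/2, 0 and +R/2, where R is the span; total SD held at 6. An interval-based decision (two one-sided tests, equivalent to a 90% interval) is also assumed. It matches the hypotheses and formula in the sample size section, although the written criterion names no interval.

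**1. The plan's own figure.** The stated formula (noncentral t, 2n − 2 degrees of freedom, true difference 0) gives 55 as the smallest n per group, with power 80.9%. The stated 55 is reproduced.

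**2. Center variance removed.** The between-center variance is 2(R/2)²/3 and the residual SD is √(36 − that variance). The 90% half-width is 1.659 × SD × √(2/55).

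| Span R | Center variance | Share of 36 | Residual SD | 90% half-width | Power, true difference 0 |
|---|---|---|---|---|---|
| none removed | – | – | 6.00 | 1.90 | 81% |
| 3 | 1.50 | 4% | 5.87 | 1.86 | 83% |
| 4 | 2.67 | 7% | 5.77 | 1.83 | 85% |
| 6 | 6.00 | 17% | 5.48 | 1.73 | 89% |

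The two degrees of freedom spent on center (106 instead of 108) do not change these figures at the precision shown. At the true difference implied by the plan's assumed means (12.0 − 10.9 = 1.1), power is 62.6% without adjustment and 64%, 66% and 70% with it.

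**3. Size of the chance shift if allocation is unstratified.** In 200,000 random 55:55 splits over three near-equal centers, the shift in the mean difference had SD 0.16, 0.31 and 0.47 oocytes for R = 2, 4 and 6. Its 95% limits were 0.31, 0.62 and 0.93 oocytes (9%, 18% and 27% of 3.4). Its mean is zero. For comparison, the standard error of the difference is 6 × √(2/55) = 1.14.

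**4. Error rate and power** (15,000 simulated trials per setting; type I error is at a true difference of 3.4, nominal 5%; power is at zero difference).

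| Allocation | R | Type I, no center term | Type I, center term | Power, no center term | Power, center term |
|---|---|---|---|---|---|
| Unstratified | 2 | 4.8% | 4.7% | 81.5% | 81.4% |
| Unstratified | 4 | 4.9% | 4.9% | 80.7% | 83.7% |
| Unstratified | 6 | 4.6% | 4.6% | 80.9% | 88.0% |
| Stratified | 2 | 4.8% | 5.2% | 81.5% | 82.0% |
| Stratified | 4 | 4.1% | 5.2% | 82.0% | 83.8% |
| Stratified | 6 | 3.4% | 5.2% | 84.6% | 88.8% |

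The unadjusted test on an unstratified trial keeps its error rate and its planned power. On a stratified trial it becomes conservative as the center span grows. Adding center restores the nominal level there and gains power wherever center matters. Most of the gain comes from the model: at R = 6, adjustment without stratification reaches 88.0%, and stratification adds less than one point.

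**The case against.** The strongest case on the other side is that nothing here is wrong. Chance center imbalance is mean-zero error, and an SD of 6 for total variation already contains any center variance. The planned test therefore holds its level and its planned power. This stands, and it means that the equivalence conclusion is not threatened.

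A reader might infer three stronger things that the documents do not support:

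- **That randomization is not stratified.** The text is silent. An IWRS can hold a stratified list, and nothing rules one out.
- **That each center uses its own operators and laboratory, and that local investigators decide when stimulation ends.** The first is a natural inference for ultrasound-guided puncture at three sites, but it is not stated. The second is not stated in the visit procedures. Dose adjustment is tied to a written follicle-size trigger.
- **That center imbalance biases the difference or raises the risk of a false equivalence claim.** The simulated error rates show no inflation. Counting the chance shift and the wider interval as two separate harms would count one source of variance twice.

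It is also fair that the gain is modest. Over the assumed spans of 3 to 6 oocytes the half-width falls by 0.04 to 0.17 oocytes, about 1-5% of the margin, and at a span of 2 the model gains almost nothing. Blocking within centers has its own cost: only the embryologist is described as blinded, so staff who know past allocations could predict later ones more easily.

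What remains is that the unadjusted comparison is the stated method. A model with center does no worse to any material extent in the settings examined, and it is valid whether or not the IWRS stratifies.

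**Conclusion.** The point holds as a gap in the description of randomization and an inexpensive improvement in efficiency. The documents do not state whether allocation is stratified by center, and the primary comparison leaves center out for an endpoint that plausibly varies by center.

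For assumed center means spanning 3 to 6 oocytes, adjustment narrows the 90% interval half-width from 1.90 to about 1.86-1.73 and raises power at zero true difference from about 81% to about 83-89%. If the IWRS stratifies and the analysis does not adjust, the test is conservative (simulated type I error 3.4% against 5% at a span of 6).

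These sizes rest on the assumed center means, near-equal centers, total SD 6 and an interval-based decision. They are not estimates for this trial.

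**What to change.** 1. **Analysis text.** Estimate the primary mean difference and its confidence interval from a linear model with treatment and center, and compare that interval with ±3.4. Fix this before unblinding. Show the difference by center descriptively.
2. **Randomization text.** State the scheme: list type, any stratification factor and the approach to blocking. If center is not already a factor, stratify the IWRS by center with varying block sizes.

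**Cost.** One or two sentences, an IWRS setting if stratification is added, and two of 108 degrees of freedom. Stratified blocks make allocation within a center slightly more predictable; varying the block size reduces this but does not remove it. If enrolment has begun, item 1 alone captures most of the benefit.

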
Safety evaluation criteria:
	
 • Incidence of serious adverse events such as severe ovarian hyperstimulation syndrome (%). • Incidence of detection of autoantibodies to the studied FSH products (%); titer of autoantibodies to anti-FSH, study/reference product, in case of a change in the level of the end point "1" in comparison with the point "0". • Incidence of the adverse reaction of ectopic pregnancy (%). • Incidence of the adverse reaction of multiple pregnancies (%). • Incidence of other adverse reactions and serious adverse reactions (%) and their severity at all stages of the patient's participation in the clinical study. • Incidence of topic and constitutional adverse reactions associated with the use of PI/PR (according to the Instructions for Medical Use, and unforeseen reactions) (%). • Incidence of clinically significant changes in laboratory parameters (%). • Incidence of clinically significant changes in the data of physical examinations and indicators of HR, BP, RR, body temperature (%).

	
 • Acceptability of the treatment, which will be estimated by the proportion of patients excluded from the study due to AEs/adverse reactions.

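### The general clinical safety criteria count adverse reactions, with no all-cause adverse-event incidence and no blinded causality assessment described

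*Combined protocol and SAP*

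**What the plan says.** Four lines under Safety evaluation criteria are worded as adverse reactions:

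- the general line, "Incidence of other adverse reactions and serious adverse reactions (%) and their severity at all stages";
- "Incidence of the adverse reaction of ectopic pregnancy";
- the matching line for multiple pregnancy;
- a line on local and systemic "adverse reactions associated with the use of PI/PR".

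The other lines carry no such wording. They are "Incidence of serious adverse events such as severe ovarian hyperstimulation syndrome", antibodies to FSH, "Incidence of clinically significant changes in laboratory parameters", clinically significant changes in physical examination and vital signs, and the proportion of patients excluded because of adverse events or reactions. On antibodies, the footnote to the visit schedule says: "The presence of anti-FSH antibodies will be determined centrally".

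Study design describes a "multicenter randomized embryologically blinded parallel group comparative therapeutic equivalence study". The Visit 5 procedures place the masking there: "Blinding of the studied therapy at the stage of oocyte counting performed by the embryologist". No other role is described as blinded.

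The visit procedures register adverse events together with reactions from Visit 2 to Visit 5, and adverse events alone from Visit 6 to Visit 9.

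**The concern.** Events and reactions are not usually the same count. An event normally becomes a reaction when someone judges that the drug caused it. If that person knows the arm, the judgement can lean either way: a new product may be blamed more readily, or its events may be put down to the IVF procedure. A difference in reaction rates then mixes the drug's effect with opinion about the drug, and a similarity in reaction rates may hide a difference in events.

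Comparative safety is one of the two study objectives and supports the biosimilarity goal. Ectopic and multiple pregnancy show the difficulty most clearly. They can be recognised only after embryo transfer, when the visits register adverse events, yet their criteria ask for adverse reactions. Two analysts could count the same ectopic pregnancy differently.

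**Working it through.** **Which criteria depend on the word reaction**

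| Safety criterion | Worded as | Causality wording |
|---|---|---|
| Serious events such as severe hyperstimulation | event | no |
| Antibodies to FSH | laboratory finding, central | no |
| Ectopic pregnancy | adverse reaction | possible |
| Multiple pregnancy | adverse reaction | possible |
| Other adverse and serious adverse reactions | adverse reaction | possible |
| Local and systemic reactions to test or reference product | adverse reaction | explicit |
| Laboratory changes | clinically significant change | no |
| Examination and vital-sign changes | clinically significant change | no |
| Exclusions | events or reactions | no |

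A non-serious clinical event judged unrelated therefore enters a between-arm incidence only if it also appears as a laboratory, examination or vital-sign change, or leads to exclusion. No line covers all adverse events.

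**Who judges, and whether blinded.** At Visit 2 patients are allocated to groups identified by product, and the stimulation protocol is prescribed. Masking is introduced at Visit 5, by coding the drug data in the record that the embryologist views. No causality step or assessor is defined. The nearest text is item 8 of the second list headed Exclusion criteria, which leaves to the investigator whether a concurrent illness is unconnected with medication.

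**Illustration.** The plan states no figure on this point to reproduce. From the documents: 55 patients per arm (Planned number of patients); Fisher's exact test and a two-sided 0.05 level (Statistical processing of data). Assumed: the true all-cause event rate, equal in both arms, and the share of events attributed to the drug in each arm.

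Reaction rate = event rate × share attributed. With a 30% event rate:

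- 0.30 × 0.50 = 15%, and 0.15 × 55 = 8.25 patients;
- 0.30 × 0.30 = 9%, and 0.09 × 55 = 4.95 patients.

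A single result of 8/55 v 5/55 gives Fisher p = 0.56.

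The chance of p < 0.05 is the sum of the binomial probabilities of all pairs of counts that the test calls significant. There is no true difference in events in any row:

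| Event rate, both arms | Attribution | Reaction rates | Chance of p < 0.05 on reactions | Same, on all events |
|---|---|---|---|---|
| 20% | 50% v 30% | 10% v 6% | 5.2% | 2.7% |
| 20% | 60% v 40% | 12% v 8% | 5.2% | 2.7% |
| 20% | 70% v 30% | 14% v 6% | 17.5% | 2.7% |
| 30% | 50% v 30% | 15% v 9% | 9.3% | 3.1% |
| 30% | 60% v 40% | 18% v 12% | 8.6% | 3.1% |
| 30% | 70% v 30% | 21% v 9% | 31.9% | 3.1% |
| 40% | 50% v 30% | 20% v 12% | 13.6% | 3.0% |
| 40% | 60% v 40% | 24% v 16% | 12.3% | 3.0% |
| 40% | 70% v 30% | 28% v 12% | 46.4% | 3.0% |

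**Masking, also assumed.** Let true event rates be 40% v 20%, with attribution of 40% v 60%. Reaction rates become 0.40 × 0.40 = 16% and 0.20 × 0.60 = 12%. The chance of a significant result is 56% on all events and 5% on reactions.

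**The case against.** The strongest reply is that the documents never define an adverse reaction, describe no causality step and name no assessor. The term may simply be loose. A separate line is limited to reactions associated with the products, a qualifier that would add little if every reaction were already drug-related. Ectopic and multiple pregnancy carry the label as categories, and the natural intention is to count each one. This stands: the causality filter is one reading of the text, not a stated rule. It does not remove the point, because the plan gives no means of choosing between the readings, and elsewhere it names events and reactions side by side as if they differed.

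A reader might go further and infer that the whole safety comparison rests on the treating investigator's opinion of causality. The documents do not support that. Serious adverse events, severe hyperstimulation among them, carry no causality wording; nor do antibodies, laboratory, examination and vital-sign changes, or exclusions. No text makes the investigator the causality assessor. Nor do the documents show that ectopic or multiple pregnancies would drop out of their own criteria, only that they could.

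It is also fair to say that the larger figures above need strongly different attribution between arms, that the stated equivalence criterion uses oocyte number alone, and that no data are lost, since adverse events are registered throughout.

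**Conclusion.** The point holds for the general clinical safety criteria. As worded, they allow the comparison of non-serious clinical events, and the counts of ectopic and multiple pregnancy, to depend on a relatedness judgement for which no blinding is described, and no all-cause incidence stands beside them. This rests on reading an adverse reaction as an event judged drug-related, which is the usual sense but is not defined here.

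The size cannot be taken from the documents. Under the assumed rates, with no true difference, reaction rates differ by 4 to 16 percentage points, and the chance of a spurious significant difference is about 5% to 46%, against about 3% on all events. The modest cases are unlikely to reach significance in one trial, but the reported incidences would still be distorted. The primary equivalence conclusion is untouched. The change is worth making because a stated objective is affected and the better comparison uses data already collected.

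**What to change.** Under Safety evaluation criteria:

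1. Make the between-arm comparison the incidence of all adverse events and of all serious adverse events registered from first dose to last visit, regardless of causality.
2. Count every ectopic pregnancy and every multiple pregnancy, whether or not it is judged related.
3. Define adverse reaction, state who assesses causality and whether that person knows the arm, and report adverse reactions in a secondary table.

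The cost is a change of wording and one more table, with no new procedure or patient. The downside is that headline incidences will be higher and will include background events of the IVF procedure; the secondary table keeps the attributed view available.

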Ethical and legal aspects:	
This study will be conducted in strict accordance with the clinical study protocol and the following international and Russian documents:
 
 1. Principles of the World Medical Association Declaration of Helsinki (Fortaleza, Brazil, 2013). 2. ICH Harmonised Tripartite Guideline (ICH E6). 3. Constitution of the Russian Federation. 4. Federal Law “On the fundamentals of protecting the health of citizens in the Russian Federation” dated November 21, 2011 No. 323-FZ, 2011. 5. Federal Law “On the Circulation of Medicines” No. 61-FZ dated 12 April 2010. 6. National standard of the Russian Federation GOST R52379-2005 “Good Clinical Practice”. 7. Decree of the Government of the Russian Federation “On approval of typical rules for the compulsory insurance of life and health of the patient involved in clinical study of medicinal product for medical use” N 714 dated September 13, 2010. 8. Order of the Ministry of Health and Social Development of the Russian Federation "On the ethics council" No. 986n dated November 29, 2012. 9. Federal Law "On personal data" No. 152-FZ dated July 27, 2006.

	
10. Order of the Ministry of Health of the Russian Federation "On the use of assisted reproductive technologies, contraindications and limitations to their use" No. 107 n dated August 30, 2012.
 
11. Federal State Budgetary Institution "Scientific Center for Expertise of Medical Products" of the Ministry of Health of Russia - Guidance on the examination of medicines, Volume 1, 2013.
 
12. Federal State Budgetary Institution "Scientific Center for Expertise of Medical Products" of the Ministry of Health of Russia - Guidance on the examination of medicines, Volume 4, 2014.
 
13. Guidance on the examination of medicines. Volume 3. - M.: POLYGRAPH-PLUS, 2014 - P. 344

Study goals:	
Confirm the biosimilarity of Primapur[®] (follitropin alfa), a solution for subcutaneous administration, and reference GONAL-F[®] (follitropin alfa), a solution for subcutaneous administration, for the controlled superovulation induction in programs of assist reproductive technologies.
 
Final goal: Authorization of Primapur[®] (follitropin alfa), a solution for subcutaneous administration for clinical use in in programs of assist reproductive technologies in the territory of the Russian Federation.

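### The 12 secondary efficacy endpoints of a biosimilarity trial get only tests of no difference, with no between-arm estimate or interval, so they cannot support similarity; pregnancy is the clearest case

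*Combined protocol and SAP*

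**What the plan says.** The Study goals section of the combined protocol and SAP sets the aim: "Confirm the biosimilarity of Primapur" with the reference product. Study type and Study design both describe a therapeutic equivalence study. The planned size is "110 female patients randomized into two equal groups of 55 subjects".

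Efficacy evaluation criteria lists one primary endpoint, the number of aspirated oocytes, and 12 secondary endpoints. Five of these are quantitative: follicles of at least 16 mm, mature oocytes, fertilized oocytes, total FSH dose and days of stimulation. Seven are counts or proportions of patients, including biochemical and clinical pregnancy.

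Statistical processing of data gives one general set of comparison methods:

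- "In order to compare two groups of normally distributed quantitative data, the Student's t-test will be used".
- Otherwise, "if quantitative data distribution differs from normal values, the Mann-Whitney U test will be used".
- "For intergroup comparisons by qualitative characteristics", Fisher's exact test is used. The same sentence adds a Bonferroni correction for multiple hypotheses, without saying which hypotheses form the family.
- Significance is two-sided p<0.05.

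The planned summaries are per arm: mean and SD, median and interquartile interval, or frequencies and percentages. The only equivalence criterion is ±3.4 oocytes, for the primary endpoint. No secondary endpoint has a margin, expected value, SD, power statement, between-arm estimate or interval.

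**The concern.** For oocyte number the plan puts the burden of proof where a similarity trial needs it: the null hypothesis is non-equivalence, and the data must reject it. For the secondary endpoints it reverses that burden. The null is no difference, and a small or noisy dataset leaves it standing. Failure to reject says nothing about how large a difference the data still allow.

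Bonferroni pushes the same way. It guards against false claims of difference, which are not the main risk here, and it makes a non-significant result easier to obtain.

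At stake is the supporting evidence. The p-value is the only between-arm result the plan calls for on pregnancy, mature oocytes and dose. It does not let a reader separate two products that behave alike from a trial too small to tell.

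**Working it through.** **Inputs from the documents.** 55 per arm, 1:1; two-sided 0.05; margin d = 3.4 oocytes; SD 6; power at least 80%; 12 secondary endpoints.

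**Assumptions.** Reference pregnancy rates of 30%, 40% and 50%, and a Bonferroni family of 12, giving 0.05/12 = 0.0042 per test. The documents give neither. Continuous endpoints are expressed in SD units because no SD is given for them.

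**1. The plan's own figure.** Calculation of sample size uses two one-sided tests with the non-central t. With a true difference of 0, the non-centrality is ±3.4·√55/√(2·6²) = ±2.97 on 108 degrees of freedom. At 0.05 per side, power is 80.9%, and 55 is the smallest n per arm that reaches 80%. The stated 55 is reproduced. It was chosen for oocyte number only.

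**2. Pregnancy, Fisher's exact test.** Power is the sum of Bin(x; 55, p₁)·Bin(y; 55, p₂) over all pairs (x, y) whose two-sided Fisher p-value is below alpha.

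| Rates compared | Drop (points) | Power at 0.05 | Power at 0.05/12 |
|---|---|---|---|
| 30% v 20% | 10 | 17% | 3% |
| 30% v 15% | 15 | 38% | 11% |
| 30% v 10% | 20 | 68% | 33% |
| 40% v 30% | 10 | 15% | 2.5% |
| 40% v 25% | 15 | 32% | 8% |
| 40% v 20% | 20 | 56% | 22% |
| 50% v 40% | 10 | 13% | 3% |
| 50% v 35% | 15 | 28% | 8% |
| 50% v 30% | 20 | 49% | 19% |

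A 15-point drop is missed more often than found at every assumed rate. The drop detected with 80% power at unadjusted 0.05 is about 23 to 28 points. The test is also conservative: with equal rates of 30-50%, its actual type I error is about 3%.

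The table assumes all 55 per arm contribute. If 27% of them did not (an assumption that borrows the plan's drop-out figure; 55·0.73 ≈ 40 per arm), power for 40% v 25% would fall from 32% to 22%.

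**3. What an interval would show.** With equal true rates p, the 95% half-width for the risk difference is 1.96·√(2p(1−p)/55): 17.1 points at 30%, 18.3 at 40% and 18.7 at 50%.

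As an illustration, take 19/55 v 11/55 (34.5% v 20.0%, a difference of 14.5 points). Fisher's p is 0.13, so the result is not significant. The Newcombe 95% CI for the difference runs from −2 to +30 points. The plan asks for the first result and not the second.

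**4. Continuous endpoints, t-test.** For a true gap of δ SDs the non-centrality is δ·√(55/2), on 108 degrees of freedom.

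| Gap (SD) | Power at 0.05 | Power at 0.05/12 |
|---|---|---|
| 0.3 | 34% | 9% |
| 0.4 | 55% | 21% |
| 0.5 | 74% | 38% |
| 0.54 | 80% | 47% |
| 0.8 | 99% | 89% |

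Unadjusted, only gaps below about 0.4 SD are more likely missed than found. Under Bonferroni over 12, a 0.5 SD gap is also more likely missed, and 80% power needs about 0.73 SD.

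**The case against.** The strongest reply is that these endpoints decide nothing. The plan ties the equivalence conclusion to oocyte number against ±3.4, and sets hypotheses and sample size for that endpoint only. A reader might infer that p≥0.05 on a secondary endpoint will be taken as similarity. No section says so, and the point does not rest on that reading. What remains is that the plan supplies no other between-arm result for these endpoints and does not rule that reading out.

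A reader might also infer that large gaps in mature oocytes or dose would probably go unseen. The arithmetic does not support this at the unadjusted level: power is 80% at 0.54 SD and 99% at 0.8 SD. With no SD in the documents, these gaps cannot be converted to oocytes or IU. That objection stands and limits the point for continuous endpoints.

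Nor would the secondary results be uninterpretable. Intervals for risk differences can be rebuilt from the counts, and those for mean differences from mean, SD and n. Some information is lost where only the median and interquartile interval are shown. The defect lies in what is planned as the comparison, not in missing raw information.

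Finally, intervals will not change the trial's conclusion, and for pregnancy they will be too wide to exclude a 15-point gap. That is true. It is a reason to show the width and call the comparison descriptive, not to report a p-value in its place.

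**Conclusion.** The concern holds in a limited form. In a trial meant to confirm biosimilarity, the 12 secondary efficacy endpoints are compared only by tests of no difference, with no between-arm estimate or interval. Such tests cannot support similarity, and Bonferroni makes non-significance easier to reach.

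Pregnancy is the clearest case: at 55 per arm a 15-point drop is detected about 28-38% of the time unadjusted, and about 8-11% under Bonferroni. This rests on assumed reference rates of 30-50%, an assumed family of 12, and all 55 per arm contributing. Continuous endpoints are affected only for gaps below about 0.4 SD, or for moderate gaps under Bonferroni.

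The primary equivalence conclusion does not depend on this. It is a worthwhile, cheap improvement to the supporting evidence, not a threat to the main result.

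**What to change.** In Statistical processing of data, under the description of methods:

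- Make the between-arm difference with a two-sided 95% CI the main result for each secondary efficacy endpoint: risk difference with a Newcombe interval for proportions, and difference in means for counts, dose and days.
- Do not apply Bonferroni to these intervals.
- State that p≥0.05 is not evidence of similarity.
- Label the biochemical and clinical pregnancy comparisons as descriptive.

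No secondary margin is needed. The cost is SAP wording and table shells; sample size, conduct and primary analysis stay as they are. The downside is that wide pregnancy intervals, about ±17 to 19 points, will be visible in the report. For scale, a formal margin test on pregnancy (one-sided 0.025, 80% power, equal rates of 30-40%, all assumed) would need 147 to 168 per arm for a 15-point margin. The descriptive label is therefore the realistic choice at 55 per arm.
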